9.2.1.2. Suspected Unexpected Serious Adverse Reactions

Suspected unexpected serious adverse reactions (SUSARs) are serious events that are not listed in the IB and that the investigator reports as related to IP or procedure. Lilly has procedures that will be followed for the recording and expedited reporting of SUSARs that are consistent with global regulations and the associated detailed guidances.

9.2.2. Complaint Handling

Lilly collects product complaints on IPs and drug delivery systems used in clinical studies in order to ensure the safety of study participants, monitor quality, and to facilitate process and product improvements.

Subjects should be instructed to contact the investigator as soon as possible if he or she has a complaint or problem with the IP or drug delivery system so that the situation can be assessed.

The investigator or his/her designee is responsible for handling the following aspects of the product complaint process in accordance with the instructions provided for this study:

- recording a complete description of the product complaint reported and any associated AEs using the study-specific complaint forms provided for this purpose
- faxing the completed Product Complaint Form within 24 hours to Lilly or its designee

If the investigator is asked to return the product for investigation, he/she will return a copy of the Product Complaint Form with the product.

9.3. Treatment of Overdose

For the purposes of this study, an overdose of ixekizumab is considered any dose higher than the dose assigned through randomization. Syringes used in this study can deliver only 1 mL volume of ixekizumab.

There is no specific antidote for ixekizumab. In the event of an overdose, the subject should receive appropriate supportive care and any AEs should be documented.

Refer to the Taltz Product Label.

9.4. Safety

Safety will be assessed throughout the course of the study at site visits and via telephone calls in between site visits.

9.4.1. Laboratory Tests

For each subject, clinical laboratory tests detailed in [Appendix 2](#) should be conducted according to the Schedule of Activities (Section 2).

9.4.2. Vital Signs

For each subject, vital signs measurements should be conducted according to the Schedule of Activities (Section 2).

Blood pressure and pulse rate should be measured after at least 5 minutes sitting.

Unscheduled orthostatic vital signs should be assessed, if possible, during any AE of dizziness or posture-induced symptoms. If orthostatic measurements are required, subjects should be supine for at least 5 minutes and stand for at least 2 minutes. If the subject feels unable to stand, supine vital signs only will be recorded.

Additional vital signs may be measured during each study period if warranted.

9.4.3. Electrocardiograms

For each subject, a single 12-lead ECG should be collected according to the Schedule of Activities (Section 2).

Electrocardiograms must be recorded before collecting any blood samples. Subjects must be supine for approximately 5 to 10 minutes before ECG collection and remain supine but awake during ECG collection. Electrocardiograms may be obtained at additional times, when deemed clinically necessary. All ECGs recorded should be stored at the investigational site.

Electrocardiograms will be interpreted by a qualified physician (the investigator or qualified designee) at the site as soon after the time of ECG collection as possible, and ideally while the subject is still present, to determine whether the subject meets entry criteria at the relevant visit(s) and for immediate subject management, should any clinically relevant findings be identified.

9.4.4. Temperature

Body temperature (oral) will be assessed at the times indicated in the Schedule of Activities (Section 2).

9.4.5. Other Tests

9.4.5.1. Injection-Site Assessments

Injection-site assessments will be performed at the times indicated in the Schedule of Activities (Section 2).

If the investigator determines that the ISR is clinically significant, or if a subject indicates symptoms are indicative of an ISR (unsolicited event; volunteered by subject), the event will be captured as an AE.

Induration, swelling, pruritus, and erythema/redness associated with study injection sites will be evaluated by the investigator or designee.

9.4.5.2. Bleeding/Bruising Assessment

All injection sites will be observed at the times indicated in the Schedule of Activities (Section 2) by the investigator or designee, and the presence of visible bleeding/bruising will be recorded on the eCRF. A bandage may be placed on the injection site after assessment.

9.4.5.3. Injection-Site Pain

Pain measurements will be quantified using the 100-mm VAS pain score for all subjects. The VAS is a well-validated tool (Williamson and Hoggart 2005) to assess injection-site pain; it is presented as a 100-mm line anchored by verbal descriptors, usually “no pain” and “worst imaginable pain.” The subject will be asked to relate any pain at the injection site on a scale of 1 to 100 mm on the line immediately (within 1 minute) following injection and at the additional time points listed in the Schedule of Activities (Section 2).

9.4.5.4. Columbia Suicide Severity Rating Scale

Columbia Suicide Severity Rating Scale (C-SSRS): A scale that captures the occurrence, severity, and frequency of suicidal ideation and/or behavior during the assessment period. The scale includes suggested questions to solicit the type of information needed to determine if suicidal ideation and/or behavior occurred. Any occurrence of suicide-related thoughts and behaviors will be assessed at the times indicated in the Schedule of Activities (Section 2) using the C-SSRS. The C-SSRS is administered by an appropriately trained healthcare professional with at least 1 year of patient care/clinical experience.

The nonleading AE collection should occur prior to the collection of the C-SSRS. If a suicide-related event is discovered during the C-SSRS but was not captured during the nonleading AE collection, sites should not change the AE form. If an event is serious or leads to discontinuation, this is an exception where the SAE and/or AE leading to discontinuation should be included on the AE form and the process for reporting SAEs should be followed. The first time the scale is administered in this study, the C-SSRS ‘Baseline – Screening’ version will be used, and the findings will constitute the baseline assessment. The C-SSRS ‘Since Last Visit’ scale will be used for all subsequent assessments. The Lilly Self-Harm Supplement should be completed every time the C-SSRS is administered. If there are positive findings on the Self-Harm Supplement, then the Lilly Self-Harm Follow-Up form will be used to collect additional information to allow for a more complete assessment of these behaviors.

9.4.5.4.1. Hospital Anxiety Depression Scale

The HADS depression subscale is a 7-item assessment scale that determines the levels of depression that a subject is experiencing over the past week. The HADS depression subscale utilizes a 4-point Likert scale (e.g., 0 to 3) for each question and is intended for ages 12 to 65 years (Zigmond and Snaith, 1983; White et al. 1999). The score can range from 0 to 21, with higher scores indicating greater depression (Zigmond and Snaith 1983; Snaith 2003).

9.4.6. Safety Monitoring

The Lilly CP or CRP/scientist will monitor safety data throughout the course of the study.

Lilly will review SAEs within time frames mandated by company procedures. The Lilly CP or CRP will periodically review trends in safety data, laboratory analytes, and AEs.

When appropriate, the Lilly CP or CRP will consult with the functionally independent Global Patient Safety therapeutic area physician or clinical research scientist.

9.4.6.1. Hepatic Safety

If a study subject experiences elevated ALT $\geq 3 \times$ upper limit of normal (ULN), ALP $\geq 2 \times$ ULN, or elevated total bilirubin $\geq 2 \times$ ULN, liver tests ([Appendix 4](#)) should be repeated within 3 to 5 days including ALT, AST, ALP, TBL, conjugated bilirubin, gamma-glutamyl transferase, and creatine phosphokinase to confirm the abnormality and to determine if it is increasing or decreasing. If the abnormality persists or worsens, clinical and laboratory monitoring should be initiated by the investigator based on consultation with the Lilly CP or CRP. Monitoring should continue until levels normalize and/or are returning to approximate baseline levels.

Additional safety data should be collected if 1 or more of the following conditions occur:

- elevation of serum ALT to $\geq 5 \times$ ULN on two or more consecutive blood tests
- elevated serum TBL to $\geq 2 \times$ ULN (except for cases of known Gilbert's syndrome)
- elevation of serum ALP to $\geq 2 \times$ ULN on 2 or more consecutive blood tests
- subject discontinued from treatment due to a hepatic event or abnormality of liver tests
- hepatic event considered to be a SAE.

9.5. Pharmacokinetics

At the visits and times specified in the Schedule of Activities (Section 2), venous blood samples of approximately 3 mL each will be collected to determine the serum concentrations of ixekizumab. A maximum of 3 samples may be collected at additional time points during the study if warranted and agreed upon between both the investigator and sponsor. Instructions for the collection and handling of blood samples will be provided by the sponsor. The actual date and time (24-hour clock time) of each sampling will be recorded.

9.5.1. Bioanalysis

Samples will be analyzed at a laboratory approved by the sponsor and stored at a facility designated by the sponsor. Concentrations of ixekizumab will be assayed using a validated enzyme-linked immunosorbent assay method.

Bioanalytical samples collected to measure IP concentrations will be retained for a maximum of 1 year following last subject visit for the study.

9.6. Pharmacodynamics

This section is not applicable for this study.

9.6.1. Immunogenicity Assessments

At the visits and times specified in the Schedule of Activities (Section 2), venous blood samples of approximately 10 mL each will be collected to determine antibody production against ixekizumab. To interpret the results of immunogenicity, venous blood samples will be collected at the same time points to determine the serum concentrations of ixekizumab. In the event of drug hypersensitivity reactions (immediate or non-immediate), additional samples will be collected as close to the onset of the event as possible, at the resolution of the event, and 30 days following the event. Instructions for the collection and handling of blood samples will be provided by the sponsor. The actual date and time (24-hour clock time) of each sampling will be recorded.

Treatment-emergent ADAs (TE ADAs) are defined in Section 10.3.3.

Immunogenicity will be assessed by a validated assay designed to detect ADAs in the presence of ixekizumab at a laboratory approved by the sponsor. Antibodies may be further characterized and/or evaluated for their ability to neutralize the activity of ixekizumab and/or their ability to cross-react with endogenous counterparts.

Samples will be retained for a maximum of 15 years after the last subject visit, or for a shorter period if local regulations and ethical review boards (ERBs) allow, at a facility selected by the sponsor. The duration allows the sponsor to respond to future regulatory requests related to ixekizumab. Any samples remaining after 15 years will be destroyed.

9.7. Genetics

A blood sample will be collected for pharmacogenetic analysis as specified in the Schedule of Activities (Section 2), where local regulations allow.

Samples will not be used to conduct unspecified disease or population genetic research either now or in the future. Samples will be used to investigate variable exposure or response to ixekizumab and to investigate genetic variants thought to play a role in Ps. Assessment of variable response may include evaluation of AEs or differences in efficacy.

All samples will be coded with the subject number. These samples and any data generated can be linked back to the subject only by the investigative site personnel.

Samples will be retained for a maximum of 15 years after the last subject visit, or for a shorter period if local regulations and/or ERBs impose shorter time limits, for the study at a facility selected by Lilly or its designee. This retention period enables use of new technologies, response to regulatory questions, and investigation of variable response that may not be observed until later in the development of ixekizumab.

Molecular technologies are expected to improve during the 15 year storage period and therefore cannot be specifically named. However, existing approaches include whole genome or exome sequencing, genome wide association studies, multiplex assays, and candidate gene studies. Regardless of technology utilized, data generated will be used only for the specific research scope described in this section.

9.8. Biomarkers

This section is not applicable for this study.

[figure not shown]
9.9. Health Economics

This section is not applicable for this study.

10. Statistical Considerations and Data Analysis

10.1. Sample Size Determination

Up to 99 subjects may be enrolled to ensure that 78 subjects (26 for each treatment) complete the study.

Subjects who are randomized but not administered treatment may be replaced to ensure that 78 subjects (26 for each treatment) complete the study.

10.2. Populations for Analyses

10.2.1. Study Participant Disposition

A detailed description of subject disposition will be provided at the end of the study.

10.2.2. Study Participant Characteristics

The subjects' age, sex, weight, height, BMI, race, and other demographic characteristics will be recorded and summarized using descriptive statistics.

10.3. Statistical Analyses

Statistical analysis of this study will be the responsibility of Eli Lilly and Company or its designee.

Pharmacokinetic analyses will be conducted on data from all subjects who receive 1 dose of ixekizumab and have evaluable PK.

Safety analyses will be conducted for all enrolled subjects, whether or not they completed all protocol requirements.

Additional exploratory analyses of the data will be conducted as deemed appropriate. Study results may be pooled with the results of other studies for population PK analysis purposes to avoid issues with post-hoc analyses and incomplete disclosures of analyses.

10.3.1. Safety Analyses

10.3.1.1. Clinical Evaluation of Safety

All IP and protocol procedure AEs will be listed, and if the frequency of events allows, safety data will be summarized using descriptive methodology.

The incidence of symptoms for each treatment will be presented by severity and by association with IP as perceived by the investigator. Symptoms reported to occur prior to study entry will be

distinguished from those reported as new or increased in severity during the study. Each symptom will be classified by the most suitable term from the medical regulatory dictionary.

The number of IP-related SAEs will be reported.

10.3.1.2. Statistical Evaluation of Safety

10.3.1.2.1. Injection-Site Pain

VAS pain score will be summarized using standard descriptive statistics. In addition, the severity of pain will be categorized by VAS pain score as: mild pain (≤ 30), moderate pain (>30 and ≤ 70), and severe pain (>70). The number and percentage of the subjects in each pain severity category will be summarized by formulation and time point.

A mixed model for the repeating measures analysis model will be used to analyze the continuous injection-site pain VAS score. The model will include formulation and time post injection (0, 10, 20, 30, and 60 minutes) and formulation by time as fixed factors. The covariance structure of the model will be unstructured. Other covariance matrices may be explored if needed. The Kenward-Roger method will be used to estimate the denominator degrees of freedom. Type III sums of squares for the least squares means will be used for the statistical comparison; the treatment differences along with their corresponding 95% CIs will also be reported.

Additional analyses may be performed as deemed necessary.

10.3.1.2.2. Statistical Evaluation of Other Safety Parameters

Safety laboratory parameters and vital signs data will be listed and summarized using standard descriptive statistics, where possible. Injection-site assessments, including induration, swelling, pruritis, bleeding/bruising, and erythema/redness, will also be assessed. The parameters will be listed and summarized using descriptive statistics. Suicidal ideation and/or behavior and self-injurious behavior with no suicidal intent, based on the C-SSRS, will be listed by subject. Only subjects that show suicidal ideation/behavior or self-injurious behavior without suicidal intent will be included in the listing (ie, if a subject's answers are all 'no' for the C-SSRS, then that subject will not be displayed). HADS item scores will be listed for subjects with HADS depression subscale ≥ 11 at any time. Additional analysis may be performed if warranted upon review of the data.

10.3.2. Pharmacokinetic Analyses

10.3.2.1. Pharmacokinetic Parameter Estimation

Pharmacokinetic parameter estimates for ixekizumab will be calculated by standard noncompartmental methods of analysis.

The primary parameters for analysis will be C_{\max} , $AUC(0-\infty)$, $AUC(0-t_{\text{last}})$ of ixekizumab. Other noncompartmental parameters, such as time to maximum drug concentration (t_{\max}), half-life associated with the terminal rate constant in noncompartmental analysis ($t_{1/2}$), apparent clearance, and apparent volume of distribution may be reported. PK parameters may also be

normalized by body weight in the event there are differences in body weight between the treatment groups.

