	-28 to -2 days prior to Day 1	-1	1	3	5 ±1d	8 ±1d	11 ±1d	15 ±2d	22 ±2d	29 ±2d	36 ±2d	43 ±2d	50 ±2d	57 ±3d	64 ± 3d	71 ±3d	85/ED ±3d		
Informed Consent	X																		
Medical History and Demographics	X																		
Review/Confirm Inclusion/Exclusion Criteria	X	X																	
Subject Admission to CRU		X																	
Subject Discharge from CRU			X																Subjects may be discharged after completion of the 4-hour safety assessments on Day 1, at the investigator's discretion.
Outpatient Visit				X	X	X	X	X	X		X		X		X		X	X	
Safety Assessment (Telephone Call)											X		X		X				
Randomization			X																
C-SSRS Lilly Self-Harm Supplement	X	X				X				X								X	At screening 'Baseline - Screening' questionnaire to be used, all other timepoints use 'Since Last Visit' questionnaire.
HADS Depression sub-scale	X	X				X				X								X	
Height, Weight, and BMI	X																	X	Weight only at Day 85/ED.
Body Temperature (Oral)			P	X	X	X	X	X	X	X		X		X		X	X		

Procedure	Screening	Days																Comments	
	-28 to -2 days prior to Day 1	-1	1	3	5 ±1d	8 ±1d	11 ±1d	15 ±2d	22 ±2d	29 ±2d	36 ±2d	43 ±2d	50 ±2d	57 ±3d	64 ± 3d	71 ±3d	85/ED ±3d		
Physical Examination /Medical Assessment	X	X																X	Full physical examination/medical assessment at Screening. Symptom-directed examinations/assessments at other times, and as deemed necessary by the investigator.
Vital Signs (sitting) (hours)	X	X	P, 2-4					X				X						X	Day 1 2-4 hour assessment to be conducted at least 2 hours postdose and prior to discharge at approximately 4 hours postdose. Time points may be added if warranted and agreed upon between Lilly and the investigator.
Clinical Laboratory Tests	X	X						X	X									X	See Appendix 2 , Clinical Laboratory Tests, for details.
Serology	X																		See Appendix 2 , Clinical Laboratory Tests, for details.
QuantiFERON®-TB Gold Test/TST	X																		
Urine Ethanol Test and Drug Screen	X	X																	May be repeated at the discretion of the investigator.
FSH Test	X																		Females only, if applicable.
Pregnancy Test	X	X																X	Females only. Serum pregnancy test will be performed at screening. Urine pregnancy test will be performed at all other times.
Single 12-lead ECG	X																		Single Screening ECG.
Ixekizumab			X																Subjects will fast (water only

Procedure	Screening	Days																Comments

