Highly effective methods of contraception include combination oral contraceptives, implanted contraceptives, or intrauterine device or a combination of 2 effective methods of contraception (such as male or female condoms with spermicide, diaphragms with spermicide, or cervical sponges) will be used. The subject may choose to use a double-barrier method of contraception. Barrier protection methods without concomitant use of a spermicide are not a reliable or acceptable method. Thus, each barrier method must include the use of a spermicide. It should be noted that the use of male and female condoms as a double-barrier method is not considered acceptable due to the high failure rate when these methods are combined.

4) Women not of childbearing potential may participate and include those who are:

A. Infertile due to surgical sterilization (hysterectomy, bilateral oophorectomy, or tubal ligation), a congenital anomaly such as mullerian agenesis, or

B. Post-menopausal – defined as either

i. A woman at least 50 years of age with an intact uterus, not on hormone therapy, who has had either

a) spontaneous amenorrhea for at least 1 year, or

b) at least 6 months of spontaneous amenorrhea with a follicle-stimulating hormone level >40 mIU/mL, or

ii. A woman 55 years or older, not on hormone therapy, who has had at least 6 months of spontaneous amenorrhea, or

iii. A woman 55 years or older with a diagnosis of menopause prior to starting hormone replacement therapy.

[2] are aged 18 to 75 years at the time of screening.

[3] have a body mass index (BMI) of 18.0 to 32.0 kg/m², inclusive.

[4] have venous access sufficient to allow for blood sampling as per the protocol.

- [5] are reliable and willing to make themselves available for the duration of the study and are willing to follow study procedures.
- [6] are able and willing to give signed informed consent.

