7.2. Method of Treatment Assignment

Subjects will be randomly assigned to 1 of 3 treatments using a computer-generated allocation code.

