10.3.2.2. Pharmacokinetic Statistical Inference

Pharmacokinetic parameters will be evaluated to estimate the relative bioavailability of Test Formulation 1 and Test Formulation 2 compared to the commercial formulation (Reference). Log-transformed C_{\max} and AUC parameters will be evaluated in a linear mixed-effects model with a fixed effect for formulation and a random effect for subject. The treatment differences will be back-transformed to present the ratios of geometric means and the corresponding 90% CI.

The t_{\max} will be analyzed using a Wilcoxon rank sum test. Estimates of the median difference based on the observed medians, 90% CIs and p-values from the Wilcoxon rank sum test will be calculated.

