3. INTRODUCTION

This SAP has been developed after review of the Clinical Study Protocol (final version dated 19th September 2018 and amendment a dated 15 November 2018).

This SAP describes the planned analysis of the safety, tolerability and pharmacokinetic (PK) data from this study. A detailed description of the planned TFLs to be presented in the clinical study report (CSR) is provided in the accompanying TFL shell document.

The intent of this document is to provide guidance for the statistical and PK analyses of data. In general, the analyses are based on information from the protocol, unless they have been modified by agreement between Eli Lilly and Company and Covance Early Clinical (EC) Biometrics. A limited amount of information concerning this study (e.g., objectives, study design) is given to help the reader's interpretation. This SAP must be signed off prior to first subject administration for this study. When the SAP and TFL shells are agreed upon and finalized, they will serve as the template for this study's CSR.

This SAP supersedes the statistical considerations identified in the protocol; where considerations are substantially different, they will be so identified. If additional analyses are required to supplement the planned analyses described in this SAP, they may be performed and will be identified in the CSR. Any substantial deviations from this SAP will be agreed upon between Eli Lilly and Company and Covance EC Biometrics and identified in the CSR. Any minor deviations from the TFLs may not be documented in the CSR.

This SAP is written with consideration of the recommendations outlined in the International Conference on Harmonisation (ICH) E9 Guideline entitled Guidance for Industry: Statistical Principles for Clinical Trials¹ and the ICH E3 Guideline entitled Guidance for Industry: Structure and Content of Clinical Study Reports².

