9.3 Pharmacokinetic Assessment

9.3.1 Pharmacokinetic Analysis

The PK parameter estimates will be determined using non-compartmental methods in validated software program, Phoenix WinNonlin (Certara, Version 6.4 or later):

Serum concentrations of ixekizumab and will be used to determine the following PK parameters, when possible:

Parameter	Units	Definition
AUC(0-∞)	ug.day/mL	area under the concentration versus time curve from time zero to infinity
AUC(0-t _{last})	ug.day/mL	area under the concentration versus time curve from time zero to time t, where t is the last time point with a measurable concentration
%AUC(t _{last} -∞)	%	percentage of AUC that is due to extrapolation from the last measurable concentration to infinity
C _{max}	ug/mL	maximum observed drug concentration
t _{max}	day	time of maximum observed drug concentration
t _{1/2}	day	half-life associated with the terminal rate constant (λ_z) in non-compartmental analysis
CL/F	L/h	apparent total body clearance of drug calculated after extra-vascular administration
V _{ss} /F	L	apparent volume of distribution at steady state after extra-vascular administration
V _z /F	L	apparent volume of distribution during the terminal phase after extra-vascular administration

Weight normalized PK parameters will be calculated. Additional PK parameters may be calculated where appropriate.

Any exceptions or special handling of data will be clearly documented within the final study report.

PK analysis will, where possible, be carried out using actual postdose times recorded in the raw data.

Formatting of tables, figures and abbreviations will follow the Eli Lilly Global PK/PD/TS Tool: NON-COMPARTMENTAL PHARMACOKINETIC STYLE GUIDE. The version of the tool effective at the time of PK analysis will be followed.

General PK Parameter Rules

- Actual sampling times will be used in the final analyses of individual PK parameters, except for non-bolus pre-dose sampling times which will be set to zero.
- C_{max} and t_{max} will be reported from observed values. If C_{max} occurs at more than one time point, t_{max} will be assigned to the first occurrence of C_{max}.
- AUC parameters will be calculated using a combination of the linear and logarithmic trapezoidal methods (linear-log trapezoidal rule). The linear trapezoidal method will be applied up to t_{max} and then the logarithmic trapezoidal method will be used after t_{max}. The

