9.3.2 Pharmacokinetic Statistical Methodology

PK parameters will be evaluated to estimate the relative bioavailability of Test Formulation 1 and Test Formulation 2 compared to the commercial formulation (Reference).

Log-transformed C_{max} , $AUC(0-\infty)$ and $AUC(0-t_{last})$ will be evaluated in a linear mixed-effects model with a fixed effect for formulation and a random effect for subject. The treatment differences will be back-transformed to present the ratios of geometric means and the corresponding 90% CI.

Example SAS code:

```
proc mixed data=xxx;  
  by parameter;  
  class formulation subject;  
  model log_pk = formulation / residual;  
  lsmeans formulation / alpha=0.1 cl pdiff;  
  random intercept / subject=subject;  
  ods output lsmeans=lsmeans;  
  ods output diffs=diffs;  
run;
```

The t_{max} will be analyzed using a Wilcoxon rank sum test. Estimates of the median difference based on the observed medians, 90% CIs and p-values from the Wilcoxon rank sum test will be calculated.

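### Screening body weight is measured in every subject but is left out of the primary formulation model, where a pre-specified log-weight covariate would cost little and could narrow the 90% CIs

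*Protocol*

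**What the plan says.** Each subject receives one fixed 80 mg dose in a 1:1:1 parallel design (Protocol 5.1 and 7.1). On allocation, Protocol 7.2 states: "Subjects will be randomly assigned to 1 of 3 treatments using a computer-generated allocation code". No stratification is mentioned.

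The Schedule of Activities (Protocol 2) lists "Height, Weight, and BMI" at screening. Inclusion criterion 3 requires that subjects "have a body mass index (BMI) of 18.0 to 32.0 kg/m², inclusive", so every eligible subject has a screening weight.

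Weight enters the PK plan in two places:

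- Protocol 10.3.2.1 allows parameters to be "normalized by body weight in the event there are differences in body weight between the treatment groups". It does not say what counts as a difference or how to normalize.
- SAP 9.3.1 drops the condition: "Weight normalized PK parameters will be calculated".

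Neither place gives the normalized parameters a role in inference. Protocol 10.3.2.2 analyses the log parameters in a "linear mixed-effects model with a fixed effect for formulation and a random effect for subject". The example code in SAP 9.3.2 agrees: "model log_pk = formulation / residual". SAP 3 adds: "This SAP supersedes the statistical considerations identified in the protocol". The SAP model therefore governs, and the protocol's imbalance condition does not create a second primary result.

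**The concern.** With one value per subject for each parameter, the random subject effect cannot be separated from residual error. All between-subject variability in exposure, including any part due to weight, stays in the standard error of the formulation ratio. If weight is related to exposure after a fixed dose, a covariate removes that part. It also reduces the effect of a chance weight imbalance on the estimated ratio.

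The sponsor treats weight as possibly relevant, since both documents provide for normalizing by it, yet the analysis that answers the primary objective ignores it. That objective is estimation with 90% CIs, and no sample-size rationale, CV or precision target is given (Protocol 10.1, SAP 7). CI width is therefore the main measure of what the trial delivers.

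The timing also matters. PK data may be reviewed while the study runs (Protocol 10.3.4, SAP 10), and an adjustment chosen after that carries less weight than one fixed beforehand.

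**Working it through.** **Inputs from the documents.** 26 completers per arm, 78 in total (Protocol 10.1); three parallel arms; log-transformed parameters; 90% CIs. The figure of 78 comes with no CV, margin or power, so it cannot be reproduced and is used only as an input.

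**Inputs assumed.** r is the within-arm correlation of log weight with log exposure. The documents do not give it, so a range is shown. Log weight is taken as normal.

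**Formulas.** Let s be the between-subject SD of log exposure and n = 26.

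- Unadjusted variance of a pairwise log difference: s² × 2/n, with 78 − 3 = 75 error df.
- Adjusted variance: s²(1 − r²) × (2/n) × (1 + F/75), with 74 error df. F follows an F(1, 75) distribution and reflects chance weight imbalance between the two arms. Its mean is 75/73, so the expected inflation is 1 + 1/73 = 1.0137.
- Expected width ratio, adjusted to unadjusted: [t(0.95, 74)/t(0.95, 75)] × √[(1 − r²) × 1.0137]. The t ratio is 1.00017, so the width ratio is 1.0070 × √(1 − r²).
- Break-even, where the width ratio is 1: |r| = √(1 − 1/1.0070²) = 0.118.
- Equivalent increase in subjects: 1/ratio² − 1.

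| \|r\| | Width ratio | Change in width | Equivalent extra subjects |
|---|---|---|---|
| 0 | 1.0070 | 0.7% wider | none |
| 0.2 | 0.9867 | 1.3% narrower | 2.7% |
| 0.3 | 0.9606 | 3.9% narrower | 8.4% |
| 0.4 | 0.9229 | 7.7% narrower | 17.4% |
| 0.5 | 0.8721 | 12.8% narrower | 31.5% |
| 0.6 | 0.8056 | 19.4% narrower | 54.1% |

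**Simulation check (100,000 trials per r).** The width ratios were 1.0070, 0.9866, 0.9606, 0.9230, 0.8723 and 0.8055. Coverage was 0.899 to 0.902 for both models, and mean error was about 0 for both.

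**Single-trial behaviour.** The break-even is an average over randomizations. The adjusted CI is narrower in about 20% of trials at r = 0, 40% at 0.12, 49% at 0.15, 65% at 0.2, 88% at 0.3 and 98% at 0.4.

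**Evaluable numbers.** At 20 per arm the cost is 0.9% and the break-even about 0.14. At 33 per arm they are 0.5% and 0.10.

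**In terms of slope.** r = |slope| × SD(log weight)/s, with s = √ln(1 + CV²). For an assumed CV of 30% to 40% and SD of log weight of 0.16 to 0.20:

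- |slope| 0.25: 0.2% wider to 0.8% narrower
- |slope| 0.5: 1.5% to 5.3% narrower
- |slope| 1.0: 8% to 26% narrower

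**Example.** With CV 40% and an observed ratio of 1.00, s = 0.385 and the unadjusted CI is exp(±t(0.95, 75) × 0.385 × √(2/26)) = 0.837 to 1.195. Multiplying the log half-width by the width ratio gives 0.839 to 1.192 at |r| = 0.2, 0.849 to 1.178 at 0.4 and 0.866 to 1.154 at 0.6.

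**The case against.** The strongest reply is that nothing is broken. A formulation-only model on log exposure is a legitimate pre-specified analysis, unbiased with correct coverage. The size of the benefit rests on a correlation that the documents do not give, and at the low end of the assumed range it is negligible. No equivalence margin is stated, so no conclusion is shown to turn on a narrower interval. A weight-adjusted sensitivity analysis would show the reader the same numbers.

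Much of this stands. The point concerns precision only, and the larger gains belong to the top of an assumed range. But the comparison is lopsided: a loss of about 0.7% against gains of several percent or more if weight matters moderately. A sensitivity result also cannot supply the primary interval, and it is less persuasive if chosen after PK data have been seen.

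Timing is a fair objection too. SAP 3 requires sign-off before first dosing, and the amendment (b) summary (Protocol Appendix 6) responds to a serious adverse event in this study, so dosing may already have started. A change of primary model must then be declared openly. That adds to the cost but does not remove the reason for the change.

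The shift from *may* in the protocol to *will* in the SAP is minor, and SAP 12 is not clearly wrong to report no changes. The table shells and the PK style guide, which are not available here, might define the normalization. They would not change the model in SAP 9.3.2.

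**Conclusion.** The concern holds as a recommendation on precision. The primary model omits a baseline variable that every subject has and that the sponsor already regards as possibly relevant.

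At 26 per arm, including it costs an expected 0.7% in CI width if weight is irrelevant and pays on average once |r| exceeds about 0.12. For |r| between 0.2 and 0.6 the expected narrowing is 1.3% to 19.4%. These figures assume a common slope across arms and about 26 evaluable subjects per arm. They do not depend on the CV, except in the slope ranges and the worked example. The true r is not in the documents, so the actual gain is unknown. The planned unadjusted analysis remains valid.

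**What to change.** - In SAP 9.3.2, add log screening weight as a continuous fixed effect, so that the primary model is log(parameter) = formulation + log(screening weight). Report the formulation ratios and 90% CIs from it.
- Keep the model without weight as a sensitivity analysis.
- Fix this before any PK data are reviewed, and record it in SAP 12 as a change from Protocol 10.3.2.2.
- Define the weight normalization (which parameters, which formula), state that normalized parameters are descriptive only, and align Protocol 10.3.2.1 with SAP 9.3.1.

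The cost is one covariate, one of 75 error degrees of freedom and a documented SAP amendment. No new data are needed.
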